1.2 SECONDARY STUDY OBJECTIVES

1.2.1

To estimate event free survival (EFS) (based on standard two or three-dimensional tumor measurements) for children with recurrent, refractory or progressive Juvenile Pilocytic Astrocytomas and Optic Pathway Gliomas who are treated with Peginterferon.

1.2.2

To define the toxicities of long term weekly pegylated interferon alpha-2b in pediatric patients with refractory, recurrent and progressive Juvenile Pilocytic Astrocytomas and Optic Pathway Gliomas.

1.2.3

To compare response categories and EFS across the 3 MR sequences (T2-weighted, FLAIR, T1-weighted post-contrast).

1.2.4

To evaluate the quality of life for patients with recurrent, refractory and progressive Juvenile Pilocytic Astrocytomas and Optic Pathway Gliomas who receive therapy with pegylated interferon alpha-2b

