4.3 Pegylated interferon Administration

Pegylated interferon will be administered weekly (**+/- 5 days**) at a dose of 1mcg/kg/dose via subcutaneous injection, approximately at the same time every week.

It is important to rotate the injection sites. Teaching will be done to the parents/guardian/patient in the first and/or second injection so the family will learn the technique and can continue to do it at home. Family/guardian will be provided with diaries to document compliance and side effects.

Patients may be pre-medicated with acetaminophen or ibuprofen. Specifically, patients can receive acetaminophen 10-15 mg/kg (maximum 650 mg per dose, maximum dose 4 grams/24 hours) or ibuprofen 10 mg/kg within 1 hour prior to receiving PEPegylated interferon. The patients can continue on either acetaminophen or ibuprofen for up to 48 hours after the pegylated interferon injection as needed. The maximum dose of ibuprofen in a 24-hour period will be 40 mg/kg or patients with weight for more than 45 kg is 2.4 grams/24 hours. Premedication is optional.

Pegylated interferon will begin a Cycle on Day 1 if **ANC \geq 1,000/ μ L, platelet count \geq 100,000/ μ L** (transfusion independent).

Dose calculations should be based on actual weight and adjusted as necessary prior to each cycle.

The maximum dose is 150 mcg.

Note: The calculated dose should be rounded to the nearest highest 5mcg of the prescribed dose for convenience of administration. Each cycle is 28 days. The total duration of the trial is 2 years a total of 26 cycles.

See Section 5.0 for Dose Modifications Based on Toxicities.

The therapy delivery maps (TDMs) for this cycle are on the next pages

Following completion of the first cycle, the Pegylated interferon cycle is repeated weekly for up to a total of 26 cycles, as tolerated and in the absence of disease progression (see Section 10.4 for Response Evaluation). If disease progression occurs, the patient will be taken off protocol therapy.

Subsequent Pegylated interferon cycles should begin on Day 29 or when ANC \geq 1,000/ μ L, platelet count \geq 100,000/ μ L (transfusion independent), whichever occurs later.

Therapy Delivery Plan

Pegylated interferon Dose 1mcg/kg/dose 4 consecutive weeks (28 days) will constitute one cycle. This therapy delivery map relates to all cycles of Pegylated interferon
	
Patient Name: _____ DOB _____

--	---

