-PT and PTT will be obtained at a baseline. Obtain later on only if clinically indicated.

-Endocrine Function Tests: First morning cortisol, free T4, TSH every six months or sooner if clinically indicated. Growth hormone testing to be done if clinically indicated.

-Urinalysis or urine dipstick is acceptable. Urinalysis will be obtained if urine dipstick is abnormal. If urine evaluation is normal, then check at the same time points as the brain MRI.

-Urine Pregnancy Test or Serum Pregnancy Test: required for females of childbearing potential. Additional pregnancy test per institutional guidelines. At Aflac, monthly pregnancy test for females of childbearing potential.

Radiology:

MRI of the brain/and or spine will be performed every 3 cycles throughout the duration of the treatment. Initial evaluation will be performed at the end of the cycle #3. Patients with a history of spinal disease will undergo a spine MRI at the same time points until there is no evidence of disease on 2 consecutive spine MRI's. All brain MRIs will include, if possible, diffusion-weighted, dynamic-enhanced, dynamic susceptibility, DT-MRI, and other MR sequences in addition to the standard MR sequences. All MRI's will be reviewed and interpreted with the neuroradiologist.

Quality Of Life Questionnaire:

- We have chosen the Peds-**FACT-Br**: Pediatric - For patients with Brain cancer, ages 7 to 12 year old or greater than 12 years. Additionally, we will include the parent QOL questionnaire. There are 2 versions, for patients younger than 12 years and for patients 12 years or older. To be administered prior to start therapy and q3 months at the same interval as MRIs. See appendix 2A, 2B, 2C and 2D.
- QOL questionnaires are not available for non -English speaking patients and they have not been validated in other languages. QOL questionnaires are not required for non-english speaking patients

Post-Therapy Evaluation

The following tests and procedures should be performed, if possible, at the time a patient comes off therapy, regardless of the reason for coming off therapy, unless the test or procedure has been performed in the past 14 days.

- History and physical examination.
- Performance status.
- Assessment of clinical toxicity/adverse events.
- Laboratory Assessment:
 - Complete blood count, differential and platelet count
 - SGPT (ALT), bilirubin (total and direct), BUN, creatinine, electrolytes, calcium,
 - Magnesium, phosphorus, uric acid.
 - Urinalysis

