9.3.1.2 Secondary End Points

- Time to treatment failure (Event free Survival EFS) the time from study enrollment to tumor progression, tumor recurrence, death from any cause or occurrence of a second malignant neoplasm.
- Time to death (Overall survival OS) the time from study enrollment to death from any cause.

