9.10 Radiographic Evaluation

MRI of brain with and without contrast must be performed within **30 days** prior to enrollment on the study. Patients will undergo baseline and follow-up imaging in the same scanner if possible. All patients will receive a standard MRI, unless contraindicated, performed on either the 1.5T or 3T scanner. (If MRI is contraindicated, patient cannot be enrolled). Patients undergoing MRI may also undergo additional MR sequences such as dynamic contrast-enhanced (DCE) or MRI, dynamic susceptibility contrast (DSC) MRI as time permits. These sequences are part of standard brain tumor protocols. Percent agreement between the sequences will be estimated as the number of follow-up scans in which the corresponding sequence agreed divided by the total number of follow-up scans. Standard error will be estimated by use of the bootstrap method 26 to account for the correlated dependent response data, and these values will be used to estimate the 95% confidence intervals. The event-free survival distributions will be compared across the MR sequences, with a proportional hazards model developed for dependent survival data by Wei et al (1989).

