1. The amount of tumor enhancement is quite variable in LGGs from one scan to the next. Therefore, tumor response/progression will not solely be determined by change in the amount of enhancing disease on post contrast T1 images. Measurable change in size/extent must be present on FLAIR/T2 images, or on pre-contrast T1 images.

2. Development of new disease or progression in any established lesions is considered progressive disease, regardless of response in other lesions – e.g. when multiple lesions show opposite responses, the progressive disease takes precedence.

Note:

- CT scans should not be used to determine response. For MRI imaging, the longest diameter can be measured from the axial plane or the plane in which the tumor is best seen or measured, provided the same plane and MR sequence is used in follow ups.
- The cystic components of a tumor are considered in separate tumor measurements. See options below.

Options:

- If the cyst/necrosis is eccentric, the W, T and L of the solid portion should be measured, the cyst/necrosis excluded from measurement.
- If the cyst/necrosis is central but represents a small portion of the tumor (<25%), disregard and measure the whole lesion.
- If the cyst/necrosis is central but represents a large portion of the tumor, identify a solid aspect of the mass that can be reproducibly measured.
- Leptomeningeal tumor spread is usually not a target lesion, and usually cannot be measured accurately. Presence and location of leptomeningeal tumor spread should be noted, change in extent/thickness assessed on follow up studies.
- For patients with large cystic components (>25%): One cystic component should be identified in the baseline scan. It should be measured separately from the solid component. It should be measured in 3 dimensions in the best sequence likely the T2 sequences. (L x T x W).

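### EFS cannot be compared across T2, FLAIR and post-contrast T1 as planned: progression on one sequence ends the imaging the others need, and the direction of the resulting bias cannot be known

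*Combined protocol and SAP*

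**What the plan says.** All references are to the combined protocol and SAP.

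- **Objective.** Section 1.2.3: "To compare response categories and EFS across the 3 MR sequences (T2-weighted, FLAIR, T1-weighted post-contrast".
- **Analysis.** Section 9.10: "The event-free survival distributions will be compared across the MR sequences, with a proportional hazards model developed for dependent survival data". The same section also plans percent agreement between sequences over all follow-up scans, with bootstrap standard errors.
- **Who can declare progression.** Section 10.4: "tumor response/progression will not solely be determined by change in the amount of enhancing disease on post contrast T1 images". It then adds: "Measurable change in size/extent must be present on FLAIR/T2 images, or on pre-contrast T1 images".
- **What progression does.** Section 4.3: "If disease progression occurs, the patient will be taken off protocol therapy". Sections 8.1 and 10.4 agree.
- **When scans are taken.** Section 7.1: "MRI of the brain/and or spine will be performed every 3 cycles throughout the duration of the treatment". The off-therapy tests, MRI among them, "should be performed, if possible, at the time a patient comes off therapy, regardless of the reason for coming off therapy". A test done in the previous 14 days need not be repeated. Section 7.2 points to late-effects guidelines and sets no MRI schedule.
- **The event.** Section 9.3.1.2 gives one patient-level definition of EFS: "the time from study enrollment to tumor progression, tumor recurrence, death from any cause or occurrence of a second malignant neoplasm". Nowhere does the plan define an event or a censoring rule for a single sequence.

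**The concern.** A comparison of EFS by sequence needs each sequence to be followed to its own progression. The plan does not provide for that. When T2 or FLAIR progresses first, treatment stops and so does scheduled imaging, and a later progression on post-contrast T1 is not scheduled to be seen. When post-contrast T1 progresses first, on enhancement alone, imaging carries on. T2 and FLAIR also cut each other off whenever one of them leads.

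The three sequences image the same tumor, so their progression times are very likely to be positively correlated. A patient whose post-contrast T1 follow-up ends because T2 has just progressed is then closer than average to progression on T1. Treating that patient as censored is informative censoring. The marginal model named in 9.10 gives valid standard errors for correlated event times within a patient. It does not correct for one event time being censored by another.

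At stake is the EFS half of objective 1.2.3. The trial could report a difference between sequences that the imaging schedule produced.

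**Working it through.** **1. The plan's own figures.** No size, power or precision is stated for the comparison across sequences. The only design calculation is the Simon design in section 9.2, and it reproduces. The probability of early termination at a 5% response rate is 0.95^9 = 0.630, and the expected sample size is 9 + 8 × (1 - 0.630) = 11.96. The design supplies the 17 evaluable patients used in step 5.

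**2. Inputs.** From the plan: 28-day cycles with MRI every 3 cycles, so a scan every 84 days; treatment for up to 2 years; imaging stopped by T2 or FLAIR but not by post-contrast T1. Assumed, because the plan gives no figures: the same exponential progression time on all three sequences with an 18-month median, joined by a Gaussian copula; pre-contrast T1 not modelled; each sequence censored at the scan where imaging stops.

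**3. True value.** The last 84-day scan before 24 months is the eighth, at 8 × 84 = 672 days. The median is 18 × 30.44 = 548 days. EFS = exp(-ln 2 × 672 / 548) = 0.43 on every sequence.

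**4. Estimate under the plan's stopping.** Kaplan-Meier at 24 months in a large simulated cohort (differences taken before rounding):

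| Correlation of T1 with T2/FLAIR | Correlation of T2 with FLAIR | T2 (FLAIR the same) | Post-contrast T1 | T1 minus T2, points |
|---|---|---|---|---|
| 0.5 | 0.5 | 0.50 | 0.54 | +5 |
| 0.5 | 0.7 | 0.52 | 0.53 | +1 |
| 0.5 | 0.9 | 0.54 | 0.51 | -3 |
| 0.3 | 0.7 | 0.52 | 0.49 | -3 |
| 0.7 | 0.9 | 0.54 | 0.55 | +1 |
| 0.9 | 0.9 | 0.54 | 0.60 | +6 |

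The truth is 0.43 in every cell and a difference of 0 in every row. With all correlations at zero, all three estimates return to 0.43. The bias therefore comes from dependent censoring and not from the scan interval.

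**5. Scale.** With 17 patients and no censoring, the standard error of one such estimate is √(0.43 × 0.57 / 17) = 0.12, or 12 points.

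**6. Sensitivity to the median.** Medians of 26, 52, 104 and 209 weeks were also tried. The longest is what the 5-year PFS of 42.3% quoted in section 2.2 for vinblastine implies if progression is exponential. With correlations of T1 with T2/FLAIR from 0.5 to 0.99, EFS on post-contrast T1 at week 96 was overstated by about 4 to 18 points. Between 19% and 42% of the T1 progressions that would occur within 104 weeks went unrecorded. The fitted T1:T2 hazard ratio ran from 0.83 to 1.14 when the truth was 1.0.

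**7. The other possible rule.** Suppose declared progression counts as the event on every sequence, which the patient-level definition in 9.3.1.2 would allow. The censoring bias then goes. But the sequences share most of their event times by construction, so the curves are pulled together and say little about how the sequences differ.

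**The case against.** The strongest reply is that no passage tells the analyst to censor a sequence at another sequence's progression, so the bias belongs to an assumed rule. That is correct, and the estimates above are conditional on it. It does not rescue the comparison, because the alternative in step 7 removes the bias by making the comparison uninformative.

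Three stronger readings are tempting, and the documents do not support them.

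- *The artefact always favours post-contrast T1.* A reader could infer this from the one-way rule in 10.4, but it ignores that T2 and FLAIR truncate each other. Once all three sequences are modelled, the sign depends on correlations that the trial cannot know beforehand.
- *The false difference between sequences is 7 to 11 points.* A two-sequence model with correlations of 0.5 to 0.9 gives 0.50 to 0.54 for post-contrast T1 against 0.43. That is T1 against the truth. T2 censored by FLAIR is inflated by about as much, so it is not the size of the contrast.
- *Later progressions on post-contrast T1 are never seen.* Sections 8.1 and 8.2 require follow-up data after therapy, to the fifth anniversary of enrollment at the latest, and unscheduled MRIs could catch some. Section 4.4 allows a further cycle when the investigator judges that the patient is benefiting, which conflicts with 4.3, 8.1 and 10.4. The text supports only that no later MRI is scheduled. The central review in 10.9 is not stated to add scans.

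It is also fair to say that this concerns part of one secondary objective in a small single-arm trial, and that the agreement analysis in 9.10 does not need scans after progression. Both points stand. The second is the basis of the fix.

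**Conclusion.** The concern holds in this form: the planned EFS comparison across sequences cannot be interpreted. If each sequence is censored when imaging stops, EFS is overstated on all three. Under the 18-month assumptions, 0.43 becomes about 0.49 to 0.60 on post-contrast T1 and 0.50 to 0.54 on T2 and FLAIR. The false T1-minus-T2 difference runs from about -3 to +6 points, small beside a 12-point standard error but of unknown sign and not removed by the named model. If declared progression counts on every sequence, the comparison is uninformative.

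The conclusion rests on positive correlation between sequences, which is very likely for the same tumor, and on few scans being taken after therapy ends. The sizes rest on assumed medians and correlations. The primary response endpoint and patient-level EFS are not affected.

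**What to change.** In 1.2.3 and 9.10:

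1. Make the between-sequence comparison the paired per-scan agreement that 9.10 already plans, using all scans up to and including the last on-treatment or off-therapy scan.
2. For every patient, including those with change on post-contrast T1 only, report whether and at which scan each sequence, read alone, first met the progression threshold in 10.7. Restricting this to the scan that declares progression would not do: under 10.4 that scan is selected by FLAIR/T2 or pre-contrast T1, so the asymmetry would be built back in.
3. Drop the proportional hazards comparison of EFS. If EFS by sequence is still shown, label it descriptive, define the sequence-specific event, and treat treatment-ending progression on another sequence as a competing event and not as censoring.

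Separately, section 4.4 must be reconciled with 4.3, 8.1 and 10.4 on continuing after progression, because this determines when scheduled imaging stops.

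The cost is analysis wording plus a per-sequence reading of scans that objective 1.2.3 already calls for. No scan is added. The trial gives up a formal time-to-event comparison between sequences, which its imaging schedule could not support.

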9.2 Study Design

The study is designed using Simon's two stage optimal design with a power of 80% and an alpha error of 5%. We assume an uninterested response rate of 5% and the promising response rate is 25%. In the first stage of the study, 9 eligible patients will be enrolled. If none responder among the 9 patients, the study terminates and treatment will be determined to have no improvement in the response rate. Otherwise, the study will continue with the second stage in which 8 additional eligible patients will be enrolled for a total of 17 eligible patients. At the end of total patient accrual, at least 3 of 17 eligible patients must

achieve response in order to consider the treatment interesting for further evaluation. Response is considered as either CR or PR or SD.

Optimal Two Stage Design	Optimum Design
First Stage Sample Size (n1)	9
Upper Limit For 1st Stage Rejection of Drug (r1)	0
Maximum Sample Size (n)	17
Upper Limit for 2nd Stage Rejection of Drug (r)	2
Expected Sample Size If Response Probability = P0	11.96
Probability of Early Termination at P0	0.63

9.3 Methods of Analysis:

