9.4 Analysis of Efficacy

Each patient will be classified according to their 'best response' for the purposes of analysis of treatment effect. A responder is defined as a patient who achieves a best overall response of CR or PR at any time on the study. If a patient achieves a PR or CR and later has progressive disease or relapse, then the patient will be counted as a responder. The response rate will be calculated as the ratio of the number of patients who demonstrate response (CR or PR) divided by the number of patients evaluable for response. All patients eligible for study who receive any study drug will be considered evaluable for response. Any patient who goes off protocol therapy for any reason (patient/parent/physician choice, adverse event profile, etc.) prior to the first response evaluation will be considered a non-responder. Disease progression will be based on the results of institutional review. Standard survival methods will be used for analysis of EFS and OS. Analyses include log rank tests and the product-limit (Kaplan-Meier) estimate for estimation of EFS and OS probability.

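### In its standard form, the model Section 9.10 names for comparing EFS across MR sequences has no parameter for a difference between sequences

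*Combined protocol and SAP*

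**What the plan says.** Objective 1.2.3 in Section 1.2 is "To compare response categories and EFS across the 3 MR sequences (T2-weighted, FLAIR, T1-weighted post-contrast"; all three sequences are read in the same patients. Section 9.10 handles the response-category half by percent agreement between sequences, with bootstrap standard errors and 95% confidence intervals. For the EFS half it has one sentence: "The event-free survival distributions will be compared across the MR sequences, with a proportional hazards model developed for dependent survival data by Wei et al", a source dated 1989. It gives no baseline structure, covariate, coding of sequence, hypothesis or test statistic, and the 1989 source is not among the 18 entries in Section 13.

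The other relevant text does not fill the gap. Section 9.3.1.2 defines EFS once per patient, as "the time from study enrollment to tumor progression, tumor recurrence, death from any cause or occurrence of a second malignant neoplasm". Section 9.4 says "Analyses include log rank tests and the product-limit (Kaplan-Meier) estimate for estimation of EFS and OS probability", without mentioning several times per patient. Section 9.2 fixes the size: "8 additional eligible patients will be enrolled for a total of 17 eligible patients". No effect size, event count, alpha or power is stated for the sequence comparison.

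**The concern.** The question is whether the EFS curve differs between T2-weighted, FLAIR and post-contrast T1 readings of the same patients. The method the 1989 citation points to, the Wei-Lin-Weissfeld marginal model, was built for a different question: whether covariates affect each of several failure types, allowing for correlation within a patient. If the sequences are the failure types, the model adjusts for exactly the thing the trial wants to compare.

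An analyst who follows the text literally would get no answer to the EFS half of objective 1.2.3. A substitute would then have to be chosen after the data were in hand. With so few patients, a non-significant result from that substitute could also be misread as showing that the three sequences are interchangeable for judging progression.

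**Working it through.** The plan states no figure for this comparison, so there is nothing to reproduce. The check is structural, followed by simulation under stated assumptions.

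**Inputs from the documents.** Three sequences (1.2.3); 17 eligible patients (9.2), so at most 17 clusters of three times; eight scheduled follow-up scans, before cycles 4, 7, 10, 13, 16, 19, 22 and 25 (7.1).

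**Step 1: the named model.** For sequence k the hazard is λ_k0(t)·exp(β_k′Z), with λ_k0 unspecified and separate for each k. Add a sequence effect γ_k. An event at time t on sequence k, with n_k(t) patients still at risk on that sequence, contributes to the partial likelihood

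exp(γ_k) / [n_k(t)·exp(γ_k)] = 1 / n_k(t).

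γ_k cancels in every risk set, so its score and information are exactly zero. Only the β_k remain. They describe covariates within a sequence, and 9.10 names none.

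**Step 2: a common baseline.** The same event contributes exp(γ_k) / Σ_l n_l(t)·exp(γ_l), which depends on γ.

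**Step 3: numerical check.** One simulated data set (17 patients × 3 sequences; 8, 9 and 6 events; shared gamma frailty):

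| Sequence coefficients | Log partial likelihood, separate baselines | Log partial likelihood, common baseline |
|---|---|---|
| (0, 0) | -59.606482 | -84.52 |
| (1, 0) | -59.606482 | -85.42 |
| (5, -3) | -59.606482 | -145.90 |

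With separate baselines, score and information were 0 at all three points. With a common baseline, the log hazard ratios against the reference sequence were 0.17 (robust SE 0.28) and -0.36 (robust SE 0.36).

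**Step 4: how the workable version behaves with 17 patients.** Everything here except the number of patients and scans is assumed. Times are Gaussian-copula exponential, rounded up to 12-weekly scans, with eight scans read on all sequences. One sequence has hazard ratio 0.6 for power. Tests are two-sided at 5%, with 1,500 replicates. Entries are robust 2-df Wald test / within-patient permutation test.

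| Progression by scan 8 | Correlation | Type I error | Power |
|---|---|---|---|
| 40% | 0.80 | 4.1% / 5.3% | 15.6% / 25.0% |
| 40% | 0.95 | 2.1% / 3.7% | 18.4% / 49.0% |
| 60% | 0.80 | 4.3% / 4.9% | 36.9% / 42.7% |
| 60% | 0.95 | 1.9% / 5.3% | 55.2% / 80.9% |

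Other assumptions change the picture:

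- **Weaker dependence.** At correlation 0.3 the Wald type I error was 5 to 6.5%. With gamma frailty of variance 1 (18-month median, 24 months of follow-up, 400 replicates) it was 8%, with a simulation standard error of √(0.08 × 0.92 / 400) = 1.4 points. Power there was 14%, 32% and 68% at hazard ratios 1.5, 2 and 3.
- **Whole-scan shifts between sequences.** With 60% progression and each reading unshifted with probability 0.70 or 0.85, Wald power was 8.4% and 8.5%, and permutation power 20.0% and 32.0%. At 0.85 the Wald statistic could not be computed in 13.9% of null replicates.
- **Unequal correlation, equal marginal EFS.** With T2 and FLAIR correlated 0.95, and each 0.50 with post-contrast T1, the permutation test rejected 7 to 7.5% of the time.
- **Imaging that stops at the first sequence to progress.** In a separate run of the four table scenarios, in table order, permutation power fell from 25, 52, 42 and 78% to 14, 27, 21 and 55%.

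**The case against.** The best defence is that the protocol never writes the model out. The separate-baseline form is standard knowledge of the method, not text in the document. Because the same sentence states the purpose, it can be read as a marginal Cox model with sequence as covariate and a robust variance, which does answer the question. This stands as far as it goes: the impossibility belongs to the standard form, and if the authors meant the other form the remedy is only a clarification. But nothing in 9.10, 9.4 or elsewhere says so, and a sentence is needed either way.

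A second defence is that the literal fit would fail visibly, with a singular matrix, rather than quietly report no difference; and 9.10 also plans percent agreement, which bears directly on interchangeability. Both are true and lower the stakes. They leave the EFS comparison without an analysis, and its replacement open to choice after the data are seen.

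A reader might go further and infer that the robust Wald test is always conservative, that a permutation test is simply the better replacement, or that a fixed gain in power is on offer. The documents give no progression rate, correlation or effect size to support any of these. The direction of the Wald error changes with the assumed dependence; the permutation test tests exchangeability of the within-patient times and can over-reject when sequences are unequally correlated. Section 10.4 makes unequal correlation plausible, since "tumor response/progression will not solely be determined by change in the amount of enhancing disease on post contrast T1 images".

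**Conclusion.** The point holds in limited form. As named, and in its standard form with sequence as failure type, the model cannot estimate or test a difference in EFS between sequences. That conclusion is algebraic and needs no assumption about event rates; it rests on taking the 1989 citation to mean the standard marginal model. It should not be stretched into a claim that every reading of 9.10 has zero power.

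No general power gain should be quoted. The simulated figures depend on assumed progression rates, correlations and hazard ratios, and the main table assumes complete imaging through scan 8. With at most 17 patients, the robust Wald test is conservative when sequences agree closely and near nominal or slightly anti-conservative otherwise. Power is low in many scenarios under either test.

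The consequence is confined to half of one secondary imaging objective. The primary response analysis is unaffected.

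**What to change.** Replace the last sentence of Section 9.10 with:

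> EFS by T2-weighted, FLAIR and post-contrast T1 reading will be compared in a marginal proportional hazards model with one baseline hazard common to the three sequences, MR sequence as a covariate (2 df) and a patient-clustered robust variance. A within-patient permutation test of log-rank scores will be reported as a small-sample sensitivity analysis. A non-significant result will not be taken to show that the sequences are interchangeable.

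The cost is this wording and a short program, with no new patients, scans or data. The price of the choice is a primary test whose error rate at 17 clusters is uncertain; the permutation result is a check on it, with its own exchangeability assumption.

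The change does not settle two neighbouring gaps: no sequence-specific EFS time is defined in 9.3.1.2, and it is unclear which scans will exist once progression has been declared, because progression ends protocol therapy (8.1) and the MRI schedule follows treatment cycles (7.1). Both limit what any test here can show.
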